4.2 Duration of Involvement

Total duration of involvement in the study is up to 72 days, plus a screening visit within 28 days prior to day 1 and follow up telephone call approximately 28 days after the last euglycaemic clamp.

4.3 Withdrawal of Subjects and Discontinuation Criteria

Subjects have the right to withdraw from the study at any time for any reason. The investigator also has the right to withdraw subjects from the study in the event of intercurrent illness, adverse events, protocol violations, administrative reasons or other reasons. An excessive rate of withdrawals can render the study impossible to interpret. Therefore, unnecessary withdrawal of subjects should be avoided. Should a subject decide to withdraw, all efforts will be made to complete and report the observations as thoroughly as possible.

The investigator should contact the subject either by telephone or through a personal visit or a responsible relative must be contacted to determine as completely as possible the reason for the withdrawal. A complete final evaluation at the time of the patient's withdrawal should be made with an explanation of why the subject is withdrawing from the study. If the reason for removal of a subject from the study is an adverse event or an abnormal laboratory test result, the principal specific event or test will be recorded on the Case Report Form.

A subject will be considered to have withdrawn from the study if they do not complete all euglycaemic clamp procedures (day 1, 28 and day 72).

Subjects may be replaced at the discretion of the investigator.

5. Treatment of subjects

5.1. Study Treatment Regimen

Group 1

Subjects will receive dolutegravir 50 mg once daily from day 1 for 28 days.

On the evening after the second clamp (day 28) they will cease treatment and will continue study activities for following 44 days.

Group 2

Subjects will receive no treatment from day 1 for 43 days on the day 44 they will initiate dolutegravir 50 mg once daily for 28 days (until day 72).

Dolutegravir will be dispensed by the Chelsea and Westminster NHS Trust pharmacy labelled as clinical trial supply.

5.2 Treatment Compliance

Adherence to investigational product will be evaluated using pill counts of returned / unused investigational product. This assessment will be documented in the drug accountability record.

6. Visit schedule & Procedures

The schedule of assessments is summarised in Appendix 1.

Screening Visit

The screening visit should take place within 28 days prior to study day 1.

Subjects will be provided with written information about the study in the form of a subject information sheet and will be allowed adequate time for questions and to consider the study before agreeing to participate. It will be the responsibility of the investigator or co-investigator to obtain written informed consent prior to undertaking any procedures detailed in the protocol.

The investigator or designee must provide adequate explanation of the aims, methods, objectives and potential hazards of the study. It must also be explained to the subject that they are free to refuse or withdraw from the study for any reason without detriment to their future care or treatment.

The following information and procedures will be recorded and performed as part of the screening assessments:

- Written Informed Consent
- Medical and medication history, including smoking and substance history
- Demographics; gender, ethnic origin, age, height, weight, and body mass index (BMI)
- Vital signs: temperature, blood pressure, heart rate, respiration rate, oxygen saturation
- Physical examination including measurement of waist and hip size

- Haematology complete blood count (FBC) with differential and platelet count (haemoglobin, haematocrit, erythrocyte count, white blood count, differential white blood cell count, platelets)
- Pregnancy testing and last menstrual period (LMP) date in WOCBP subjects
- Biochemistry safety labs assessment for standard clinical chemistry (glucose, creatinine, sodium, potassium, calcium, aspartate aminotransferase, alanine aminotransferase, bilirubin, CRP), including HbA1c
- HIV antibody testing, hepatitis C (antibody) and B (surface antigen) screening
- ECG
- Urinary analysis (pH, specific gravity, leucocytes, nitrite, protein, glucose, ketones, urobilinogen, bilirubin, erythrocytes) and urine drug screen

Baseline

Subjects who meet all the inclusion and exclusion criteria and wish to take part in the study will be admitted to the unit on the morning of day 1. Subjects will remain in the unit for approximately four to six hours.

The following study assessments will be performed (subjects must have fasted for at least eight hours):

- Adverse events
- Concomitant medication
- Vital signs (during the clamp procedure vital signs will occur every 30 minutes)
- Height/ weight/ BMI
- Measurement of waist and hip size
- Haematology: complete blood count (FBC) with differential and platelet count (haemoglobin, haematocrit, erythrocyte count, white blood count, differential white blood cell count, platelets)
- Biochemistry safety labs assessment for standard clinical chemistry (fasting glucose, creatinine, sodium, potassium, calcium, aspartate aminotransferase, alanine aminotransferase, bilirubin), including thyroid hormones (TSH, ft4), lipids (triglycerides, cholesterol, cholesterol HDL & LDL Sub-fractions) CRP and Hb1aC
- Urinary analysis (pH, specific gravity, leucocytes, nitrite, protein, glucose, ketones, urobilinogen, bilirubin, erythrocytes) and urine drug screen
- Pregnancy testing and LMP date in WOCBP subjects
- Adiponectin, leptin, ghrelin, testosterone
- Pituitary hormone function tests

- Dietary Questionnaire
- Sleep Questionnaires (PSQI)
- Euglycaemic clamp 1
- Insulin will be titrated 3 times during euglycaemic clamp procedure according to approved and verified formula sheet.
- ECG monitoring at 30 minute intervals during the clamp procedure
- Indirect calorimetry (all participants)

Prior to baseline visit subjects will be randomly assigned to Group 1 or Group 2:

Group 1:

- Dolutegravir 50 mg once daily for the first 28 days of the study.
- No treatment for the last 44 days of the study.

Subject will be dispensed study medication (Dolutegravir 50 mg) and instructed to self-administer the study drugs at home from the morning of day 2 until the morning prior to the next euglycaemic clamp day (Day 27).

Group 2:

- No treatment for the first 43 days of the study.
- Dolutegravir 50 mg once daily for the last 28 days of the study (day 44-72).

Subject will be dispensed study medication (Dolutegravir 50 mg) and instructed to self-administer the study drugs at home from the morning of day 45 until the morning prior to the next euglycaemic clamp day (Day 71).

Day 28

Subjects will be admitted to the unit in the morning and remain on the unit for approximately four to six hours. Group 1 subjects will take their last dose of study medication in the unit in the morning of the visit.

The following study assessments will be performed (subjects will have fasted for at least eight hours):

- Adverse events
- Concomitant medication
- Vital signs (during the clamp procedure vital signs will occur every 30 minutes)
- Height/ weight/ BMI
- Measurement of waist and hip size

- Haematology: complete blood count (FBC) with differential and platelet count (haemoglobin, haematocrit, erythrocyte count, white blood count, differential white blood cell count, platelets)
- Biochemistry safety labs assessment for standard clinical chemistry (fasting glucose, creatinine, sodium, potassium, calcium, aspartate aminotransferase, alanine aminotransferase, bilirubin), including thyroid hormones (TSH, ft4), lipids (triglycerides, cholesterol, cholesterol HDL & LDL Sub-fractions) CRP and HbA1c
- Urinary analysis (pH, specific gravity, leucocytes, nitrite, protein, glucose, ketones, urobilinogen, bilirubin, erythrocytes) and urine drug screen
- Pregnancy testing and LMP date in WOCBP subjects
- Adiponectin, leptin, ghrelin, testosterone
- Pituitary hormone function tests
- Dietary Questionnaire
- Sleep Questionnaires (PSQI)
- Euglycaemic clamp 2
- Insulin will be titrated 3 times during euglycaemic clamp procedure according to approved and verified formula sheet.
- ECG monitoring at 30 minute intervals during the clamp procedure
- Indirect calorimetry (Group 1)

Day 29 - Day 43

Wash out Period

Day 44

Subjects will be admitted to the unit in the morning and remain on the unit for approximately one to two hours. Subjects randomized to Group 2 will take their first dose of study medication in the unit in the morning of the visit.

The following study assessments will be performed (subjects must have fasted for at least 8 hours):

- Adverse events
- Concomitant medication
- Vital signs: temperature, blood pressure, heart rate, respiration rate, oxygen saturation
- Height/ weight/ BMI

- Measurement of waist and hip size
- Haematology: complete blood count (FBC) with differential and platelet count (haemoglobin, haematocrit, erythrocyte count, white blood count, differential white blood cell count, platelets)
- Biochemistry safety labs assessment for standard clinical chemistry (fasting glucose, creatinine, sodium, potassium, calcium, aspartate aminotransferase, alanine aminotransferase, bilirubin), including thyroid hormones (TSH, ft4), lipids (triglycerides, cholesterol, cholesterol HDL & LDL Sub-fractions) CRP and HbA1c
- Urinary analysis (pH, specific gravity, leucocytes, nitrite, protein, glucose, ketones, urobilinogen, bilirubin, erythrocytes) and urine drug screen
- Pregnancy testing and LMP date in WOCBP subjects
- Adiponectin, leptin, ghrelin, testosterone
- Pituitary hormone function tests
- Dietary Questionnaire
- Sleep Questionnaires (PSQI)

Day 72

Subjects will be admitted to the unit in the morning and remain on the unit for approximately four to six hours. Subjects will take their last dose of study medication (Group 2) in the unit in the morning of the visit.

The following study assessments will be performed (subjects must have fasted for at least 8 hours):

- Adverse events
- Concomitant medication
- Height/ weight/ BMI
- Vital signs (during the clamp procedure vital signs will occur every 30 minutes)
- Measurement of waist and hip size
- Haematology: complete blood count (FBC) with differential and platelet count (haemoglobin, haematocrit, erythrocyte count, white blood count, differential white blood cell count, platelets)
- Biochemistry safety labs assessment for standard clinical chemistry (fasting glucose, creatinine, sodium, potassium, calcium, aspartate aminotransferase, alanine aminotransferase, bilirubin), including thyroid hormones (TSH, ft4), lipids (triglycerides, cholesterol, cholesterol HDL & LDL Sub-fractions) CRP and Hb1aC

- Urinary analysis (pH, specific gravity, leucocytes, nitrite, protein, glucose, ketones, urobilinogen, bilirubin, erythrocytes) and urine drug screen
- Pregnancy testing and LMP date in WOCBP subjects
- Adiponectin, leptin, ghrelin, testosteron
- Pituitary hormone function tests
- Dietary Questionnaire
- Sleep Questionnaires (PSQI)
- Euglycaemic clamp 3
- Insulin will be titrated 3 times during euglycaemic clamp procedure according to approved and verified formula sheet.
- ECG monitoring at 30 minute intervals during the clamp procedure
- Indirect calorimetry (Group 2)

Follow up (Day 100)

The subject will be contacted by telephone approximately 28 days after the final euglycaemic clamp day to check whether they have experienced any adverse events. This follow up phone call should be documented in the subject's notes. WOCBP should take a home pregnancy test.

Early termination visit

If a subject withdraws or is discontinued from the study the subject should attend if at all possible for a discontinuation visit and undergo the following procedures:

- Haematology: complete blood count (FBC) with differential and platelet count (haemoglobin, haematocrit, erythrocyte count, white blood count, differential white blood cell count, platelets)
- Biochemistry safety labs assessment for standard clinical chemistry (fasting glucose, creatinine, sodium, potassium, calcium, aspartate aminotransferase, alanine aminotransferase, bilirubin), including thyroid hormones (TSH, ft4), lipids (triglycerides, cholesterol, cholesterol HDL & LDL Sub-fractions) CRP and Hb1aC
- Symptom-directed physical examination (if any adverse event experienced)

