3.3 Randomisation

After screening, eligible subjects satisfying the inclusion and exclusion criteria will be randomised 1:1 to one of two arms:

Group 1:

- Dolutegravir 50 mg once daily for the first 28 days of the study.
- No treatment for the last 44 days of the study.

Group 2:

- No treatment for the first 43 days of the study.
- Dolutegravir 50 mg once daily for the last 28 days of the study (day 44-72).

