4.1.1 Inclusion Criteria

- Willing and able to provide informed consent
- Cis-Male and Cis-Female healthy subjects without underlying conditions
- Subjects must have documented negative HIV serology by ELISA and P24 antigen and not receiving anti-HIV pre-exposure prophylaxis (PreP)
- Subjects must be clinically well volunteers aged between 18 to 60 years with BMI <30 kg/m² but >18 kg/m²
- Healthy, as determined by the investigator or medically qualified designee based on a medical evaluation, including medical history, physical examination, laboratory tests, and cardiac evaluation (including ECG)
- Non-fasting blood glucose, total cholesterol and triglycerides within normal limits
- Subjects should have complete blood count (FBC) with normal differential and platelet count (detail below of specified normal range, table 1)

Table 1 – Compete FBC with normal differential & platelets count ranges

Test	Male Normal Range	Female Normal Range
Haemoglobin (g/L)	130-168	114-150
White blood cell count ($\times 10^9$ /L)	4.2-10.6	4.2-11.2
Neutrophil count ($\times 10^9$ /L)		2.0 - 7.1
Lymphocyte count ($\times 10^9$ /L)		1.1 - 3.6
Monocyte count ($\times 10^9$ /L)		0.2 - 0.9
Eosinophil count ($\times 10^9$ /L)		0.0 - 0.5
Basophil count ($\times 10^9$ /L)		0.0 - 0.2

- A female, may be eligible to enter and participate in the study if she:
 - is of non-child-bearing potential defined as either post-menopausal (12 months of spontaneous amenorrhea and ≥ 45 years of age) or physically incapable of becoming pregnant with documented tubal ligation, hysterectomy or bilateral oophorectomy or,
 - is of child-bearing potential with a negative pregnancy test at both Screening and Day 1 and agrees to use one of the following methods of contraception to avoid pregnancy:
 - Complete abstinence from penile-vaginal intercourse. Abstinence is acceptable only as true abstinence when this is in line with the preferred and usual lifestyle of the participant;
 - Any intrauterine device with published data showing that the expected failure rate is $<1\%$ per year (not all intrauterine devices meet this criterion, see Appendix 6] for an example listing of approved intrauterine devices);
 - Male partner sterilization confirmed prior to the female subject's entry into the study, and this male is the sole partner for that subject;
 - Approved hormonal contraception (see Appendix 6] for a listing of examples of approved hormonal contraception)*;

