4.1.2 Exclusion Criteria

- Subjects with a waist hip ratio > 0.97 or BMI > 30kg/m² and BMI < 18 kg/m² will be excluded
- Acute or chronic hepatitis B infection (determined by positive hepatitis B surface antigen result at the screening visit)
- Acute or chronic hepatitis C infection (determined by positive hepatitis C antibody result at the screening visit)
- Diabetes mellitus, other metabolic syndrome or disease process in the opinion of the investigator likely to cause marked disturbance in glucose and lipid homeostasis including hypertension. Subject with HbA1c >42 mmol/mol will be excluded.
- History or presence of allergy to the dolutegravir
- ALT or AST greater than or equal to 1.5 x Upper Limit of Normal (ULN) and total bilirubin greater than or equal to 1.5 x ULN excluded;
- Pregnancy and breastfeeding women
- Alcohol consumption >10 units/week
- Clinically relevant drug use (positive urine drug screen) or history of alcohol or drug use considered by the Investigator to be sufficient to hinder compliance with treatment, follow-up procedures or evaluation of adverse events. Smoking is permitted, but tobacco intake should remain consistent throughout the study.
- Unable to refrain from the use of prescription (e.g., dofetilide) or non-prescription drugs, including vitamins, herbal and dietary supplements (including St John's wort) within 7

days (or 14 days if the drug is a potential enzyme inducer) or 5 half-lives prior to the baseline visit and throughout the study until the follow-up period, unless in the opinion of the Investigator the medication will not interfere with the study procedures or compromise participant safety.

- This includes on-going therapy with any of the following
 - Metabolically active medications
 - Any lipid-lowering medication
 - Any testosterone treatments or supplements - Glucocorticoids including inhaled steroids except for 'as necessary' use
 - Beta-blockers
 - Thiazide diuretics and indapamide
 - Thyroid preparations
 - Psychotropic agents
 - Anabolic steroids
 - Megestrol acetate
 - Dofetilide (or pilsicainide)

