11.5 Drug Accountability

The investigator will ensure that the investigational product will only be used in accordance with the protocol. Drug supplies will be kept in a secure, limited access storage area under the recommended storage conditions.

Dolutegravir 50mg will be provided by ViiV Healthcare. A drug accountability log will be kept with the investigational supplies for reconciliation purposes. This should be used to record the identification of the subject to whom the investigational product was dispensed, the date and quantity of investigational product dispensed and the quantity of investigational product unused/returned by the subject. This will be verified by the study monitor.

At the end of the study partially used or empty containers may be destroyed by pharmacy (in accordance with their usual procedures) after the study monitor has completed a final inventory.

Due to the nature of the study and the need to dose subjects outside of normal working hours, pharmacy may need to prepare and dispense investigational medicinal product to the unit in advance of baseline visit. A process is in place to retrieve investigational medicinal product for those subjects who are withdrawn after medication has been dispensed to the unit and prior to dosing.

Spare investigational medicinal product will be dispensed for replacement subjects in the event of withdrawals.

Due to the nature of the study and intensive euglycaemic days occurring outside normal working hour's pharmacy will dispense spare investigational medicinal product (IMP) to the unit. This IMP should only be used in the event of a subject failing to bring in their IMP. It is the responsibility of the investigator to release the IMP and to ensure that pharmacy is informed in order to document which subjects received the IMP. Any IMP not required will be returned to pharmacy immediately.

A specific risk assessment for the concomitant use of a Covid-19 vaccine and Dolutegravir within the current protocol was performed. The outcome is that a Covid-19 vaccine given to a trial subject enrolled into the study is a simple concomitant medication with no interaction that requires advice on timing of the vaccine or other aspects.

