Drug induced liver injury and other clinically significant liver chemistry elevations	
Non-clinical data suggested a possible, albeit low, risk for hepatobiliary toxicity with DTG. Drug-related hepatitis is considered an uncommon risk for antiretroviral therapy containing DTG regardless of dose or treatment population.
	
Subjects meeting any of the following criteria during the screening period are excluded from participating
 
 • Alanine aminotransferase (ALT) or Aspartate aminotransferase (AST) ≥ 1.5 times the upper limit of normal (ULN) or total bilirubin $\geq 1.5 \times$ULN 
Positive for HBV (hepatitis B virus surface antigen positive [+HBsAg]) or positive HCV (positive hepatitis C antibody test) within 3 months of the Day 1 study visit
 
Specific/detailed liver stopping criteria and toxicity management guidance are provided for suspected drug induced liver injury or other clinically significant liver chemistry elevations

Neural Tube Defects	
In the ongoing observational study conducted in Botswana, preliminary results show that in babies born to women who were taking DTG when
	
Pregnancy testing should be performed before initiation of DTG therapy in all women of child bearing potential (negative)

Potential Risk of Clinical Significance	Data/Rationale for Risk	Mitigation Strategy
Investigational Product: dolutegravir Refer to the most recently approved SmPC for this trial		
	
they became pregnant there was an increased risk of neural tube defects compared with the background rate.
 
Dolutegravir was tested in a complete package of reproductive toxicology studies, including embryofoetal development studies. No adverse development outcomes, including neural tube defects, were identified from reproductive toxicology studies. In reproductive toxicity studies in animals, DTG was shown to cross the placenta.
 
Data available from other sources including the Antiretroviral Pregnancy Registry (APR), other cohorts and clinical trials are insufficient to confirm or refute this potential risk.
	
pregnancy test at screening and randomization).
 
Women who are pregnant or who plan to become pregnant are excluded.
 
All women of reproductive potential should use effective contraception (Appendix 6).
 
The subject informed consent form provides information about this potential risk.

Risk Assessment: Clamp procedure

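### Allocation precedes the Day 1 visit, so women of child-bearing potential are randomised before eligibility is complete and baseline may be measured with the sequence known

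*Combined protocol and SAP*

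**What the plan says.** **Timing of allocation.** Section 6 (Baseline) states: "Prior to baseline visit subjects will be randomly assigned to Group 1 or Group 2". Section 3.3 states: "After screening, eligible subjects satisfying the inclusion and exclusion criteria will be randomised 1:1 to one of two arms". The opening of the Baseline part of Section 6 likewise treats everyone admitted on Day 1 as already meeting all criteria.

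**Eligibility that depends on Day 1.** Under Section 4.1.1 a woman may enter if she "is of child-bearing potential with a negative pregnancy test at both Screening and Day 1". Section 6 and the Appendix 1 flowchart place the second test at the baseline visit. Appendix 4 describes the requirement as a negative "pregnancy test at screening and randomization", but the flowchart has no visit between screening and baseline. The urine drug screen, a positive result of which is an exclusion under Section 4.1.2, is also repeated on Day 1. That criterion names no visit.

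**What is first measured on Day 1.** Clamp 1, indirect calorimetry, the dietary questionnaire and the PSQI are all baseline-visit assessments, and none is done at screening. Calorimetry is repeated only in Group 1 on Day 28 and only in Group 2 on Day 72, that is, only on dolutegravir.

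**Blinding, replacement and supply.** The comparator is no treatment (Section 3.2). No placebo, blinding or concealment of the sequence is described. Replacement is at the investigator's discretion (Section 4.3). Section 11.5 provides spare drug for replacement subjects and notes that "pharmacy may need to prepare and dispense investigational medicinal product to the unit in advance of baseline visit".

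**The concern.** Two things follow from this order of events.

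First, for women of child-bearing potential, one inclusion criterion cannot be checked until after allocation. A positive Day 1 test would then be a post-randomisation exclusion in a trial of 16, not a screening failure. The evaluable cohort in Section 7.2 consists only of those who complete Days 1, 28, 44 and 72, so the subject would drop out of the analysis.

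Second, every clamp, calorimetry, diet and sleep baseline is recorded after the sequence has been fixed and, as far as the text shows, possibly disclosed. Diet and sleep are self-reported, so they are the measures most open to influence. The endpoint in Section 3.1 is worded as change from baseline with dolutegravir, and the sample size statement in Section 7.1 is framed as baseline to Week 4 under dolutegravir. Day 1 is the only clamp baseline for both sequences, since no clamp is done on Day 44.

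**Working it through.** **1. The sections side by side.**

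| Place | What it implies |
|---|---|
| Section 3.3 | Randomise after screening, only subjects meeting all criteria |
| Section 6, Baseline (opening) | All criteria met before admission on Day 1 |
| Section 6, Baseline (allocation) | Group assigned before the Day 1 visit |
| Section 4.1.1 | Negative test needed at screening and on Day 1 |
| Section 6 and Appendix 1 | Second test done at the baseline visit |
| Appendix 4 | Second test done at randomisation |

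Sections 3.3 and 6 agree on timing. The conflict arises when the Day 1 test in Section 4.1.1 is added: a woman of child-bearing potential cannot both satisfy all criteria at randomisation and have one of them determined afterwards. Appendix 4 can hold only if randomisation takes place at the baseline visit, which Section 6 excludes.

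**2. Where a disturbed baseline would matter.** Let B be the Day 1 value, C2 the Day 28 value and C3 the Day 72 value. Suppose knowledge of the sequence shifts B by b in Group 1 only.

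- Within-subject contrast, Group 1: (C2 − B) − (C3 − B) = C2 − C3. Group 2: (C3 − B) − (C2 − B) = C3 − C2. B cancels, so the bias is 0.
- Dolutegravir change from baseline, pooled over both groups: bias = (8 × (−b) + 8 × 0)/16 = −b/2.
- Period-1 comparison of changes between groups: bias = −b.

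With an assumed b = 0.5 (illustrative; the documents give no value), these are 0, −0.25 and −0.50, against an equivalence margin of 1.1. A simulation of 20,000 trials gave −0.002, −0.250 and −0.499. The cancellation applies to every measure taken on both Day 28 and Day 72, including diet, sleep, lipids and hormones. Calorimetry has no control-period value, so only the second line is available to it.

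**3. The plan's power, then the effect of a Day 1 loss.** Inputs: SD of the difference 1.4 and margin ±1.1 (Section 7.1); 90% confidence interval within the margin, equal to two one-sided 5% tests (Section 7.3); true difference 0 (assumed; not stated). With n1 and n2 subjects per sequence:

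SE = 1.4 × √[(1/n1 + 1/n2)/4], with n1 + n2 − 2 degrees of freedom; power from the exact t-based calculation.

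| Split | SE | df | Power |
|---|---|---|---|
| 8/8 | 1.4 × √(1/16) = 0.350 | 14 | 82.0% |
| 8/7 | 1.4 × √[(1/8 + 1/7)/4] = 0.362 | 13 | 78.1% |
| 8/6 | 1.4 × √[(1/8 + 1/6)/4] = 0.378 | 12 | 72.7% |

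The plan's 80% with 8 per sequence is reproduced: 16 is the smallest total with at least 80% power on this calculation. One unreplaced loss takes power below 80%. Moving the allocation changes none of these inputs.

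**The case against.** The strongest reply is that this is a wording inconsistency with little statistical consequence. Much of that stands.

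- **A reader might infer that the primary comparison is biased.** It is not. The Section 7.3 model compares dolutegravir with no treatment within subjects, and the evaluable cohort has all three clamps, so the shared baseline cancels.
- **A reader might infer that ineligible subjects in general can be randomised.** Only one criterion is expressly tied to Day 1, and only for women of child-bearing potential. Such a subject would have tested negative within the previous 28 days and used contraception for at least 28 days before the first dose. No rate is given, and the repeat drug screen is not expressly an eligibility test on Day 1.
- **That the sequence is known at baseline is an inference.** No text says that subjects or staff are told. It follows from the untreated control and the lack of any concealment step. What would be known is the order, since every subject is planned to receive both conditions.
- **The measures differ in how exposed they are.** The clamp follows a feedback formula and a verified sheet, and calorimetry is gas analysis. Later questionnaires are completed with treatment known whatever happens on Day 1.
- **The calorimetry gap is mainly a separate problem.** Later allocation does not supply the missing control-period measurement.
- **The power figures show fewer completers, not allocation timing as such.** They apply only to unreplaced losses, and Sections 4.3 and 11.5 provide for replacement.
- **Section 11.5 gives an operational reason for early preparation:** dosing outside normal hours. That concerns supply and does not require the sequence to be assigned before the visit.

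What remains is a stated order of events that conflicts with the eligibility rules, together with baselines left unprotected for the summaries that depend on them.

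**Conclusion.** The point holds as a minor one. Assignment before the baseline visit cannot be squared with a Day 1 inclusion criterion, and Sections 3.3, 4.1.1 and 6 and Appendix 4 need to be reconciled.

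The possible bias is confined to dolutegravir-only changes from baseline (the endpoint as worded in Sections 3.1 and 7.1), period-1 comparisons, and calorimetry, whose only comparator is Day 1. For the pooled dolutegravir change it is half of any shift confined to one group. The documents do not allow that shift to be sized, and whether it arises depends on the sequence being disclosed before baseline is complete, which is inferred.

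The cost of a Day 1 failure is about four percentage points of power for one unreplaced subject (82.0% to 78.1%), given SD 1.4, margin 1.1 and a true difference of 0. How often this would happen is unknown. The documents do not support reading this as a threat to the primary dolutegravir-minus-control contrast or as evidence that the trial is underpowered.

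**What to change.** In Sections 3.3 and 6, state that the allocation is made or opened on Day 1, once the Day 1 eligibility results are available and all baseline measures are complete, including the questionnaires, calorimetry and clamp 1. Align Section 4.1.1, the opening of the Baseline part of Section 6 and Appendix 4 with that order. State how a subject who fails a Day 1 criterion is counted and whether she is replaced.

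This should fit the existing schedule. The synopsis already puts clamp 1 before the first study drug or untreated period, and Group 2 starts drug only on Day 44. Section 3.2, Section 6 and Appendix 1 give different times for Group 1's first dose (Day 1 afternoon, Day 2 morning, and baseline morning). Those passages must be reconciled in the same amendment.

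The cost is that allocation must be done on the day of the visit. Appendix 1 already schedules Group 1 dispensing at baseline, and Section 11.5 already allows drug on the unit in advance and its retrieval before dosing. No visit, assessment or sample size input changes.
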